The study utilizes the largest calculated sample size to ensure statistical power across all objectives. For the assessment of the Quality of Recovery (QoR-15), a cross-sectional sample of 115 patients was determined using a single mean estimation formula ($\alpha = 0.05$, $\sigma = 0.82$, $d = 0.15$). For the interventional phase, a power analysis performed via G*Power 3.1.9.4 indicated that a minimum of 54 patients (27 per group) is required to detect an effect size of 0.79 with 80% power at a 0.05 significance level. Consequently, the study aims to enroll at least 115 participants, comprising 68 elective surgery cases and 67 day-surgery cases.

6. Steps to conduct research

Phase 1: Status Assessment and Baseline Evaluation

- Conduct a retrospective cohort study to describe the ERAS implementation status in previous cases via medical records.
- Perform a cross-sectional descriptive study to evaluate the quality of postoperative recovery using the QoR-15 tool and knee function using the LKSS and the cost-effectiveness of treatment using the EQ-5D-5L tool.

Phase 2: Interventional Study and Effectiveness Evaluation

- Intervention Implementation: Apply 06 standardized ERAS measures to the patients
- Evaluate discharge readiness in the recovery unit using the Postanesthetic Discharge Scoring (PADS).
- Monitor and compare outcome variables between elective surgery and day-surgery groups, including recovery quality, complication rates, and cost-effectiveness.
- Collect data at specific intervals: Pre-op (T-1), 1-day post-op (T1), 1 month (T2), 3 months (T3), and 6 months (T4).
- Record the rate of patients requiring readmission within 7 days post-discharge.

7. Research Implementation plan (Gantt chart)

	12/25	4/2026-4/2027	05-06/27	07-12/27
Protocol				
Data collection				
Analyze data and present results				

	12/25	4/2026- 4/2027	05-06/27	07-12/27
Report				

8. References

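### The enrolment target does not equal its parts: at least 115 participants are said to be made up of 68 + 67 cases, which is 135

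*Protocol*

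**What the plan says.** Section 5 (Sample size) of the protocol sets out a rule, two calculations and a conclusion.

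- Rule: "The study utilizes the largest calculated sample size to ensure statistical power across all objectives".
- QoR-15 estimate: "a cross-sectional sample of 115 patients was determined using a single mean estimation formula", with alpha 0.05, standard deviation 0.82 and precision 0.15.
- Interventional phase: "a minimum of 54 patients (27 per group) is required to detect an effect size of 0.79 with 80% power", at a significance level of 0.05.
- Conclusion: "Consequently, the study aims to enroll at least 115 participants, comprising 68 elective surgery cases and 67 day-surgery cases".

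Section 6 (Steps to conduct research) names the same two groups as the Phase 2 comparison: "Monitor and compare outcome variables between elective surgery and day-surgery groups". It gives no numbers. Section 5 is the only place where the protocol fixes how many people are enrolled and how they divide.

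**The concern.** The last sentence of section 5 gives a total and then its two parts, and the parts do not add up to the total. The sentence is presented as following from the calculations above it, the larger of which is 115, so 115 looks like the target. Yet the group sizes imply 135. A site or sponsor team working from this text cannot tell whether 115 or 135 people are planned, or whether each group should have about 58 or about 68.

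What is at stake is a clear enrolment target and a clear split between the two groups compared in Phase 2. There is also a consequence for follow-up, which runs to 6 months. If 115 is the number enrolled and nothing is added for losses, any loss leaves fewer than the 115 calculated for the QoR-15 estimate. If 135 is the number enrolled, there is room for some loss, but the protocol does not say that this is why the figure is larger.

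**Working it through.** **Inputs, all from section 5 of the protocol.** Single mean: alpha 0.05, standard deviation 0.82, precision 0.15, stated result 115. Two groups: effect size 0.79, power 80%, alpha 0.05, stated result 27 per group (54 in total). Enrolment: at least 115, as 68 + 67. Neither the test nor its sidedness is stated. A two-sided two-sample t-test is assumed because it reproduces the stated 27.

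**1. The single-mean figure.** n = (z × SD / d)² = (1.96 × 0.82 / 0.15)² = 114.8, rounded up to 115. It reproduces.

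**2. The two-group figure.** The normal approximation gives n per group = 2 × (1.960 + 0.842)² / 0.79² = 25.2, so 26. The exact (noncentral t) calculation gives 26.15, so 27 per group and 54 in total, with 81.3% power at 27. A one-sided test would need only 21. The stated figure reproduces as two-sided.

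**3. The rule.** The larger of 115 and 54 is 115. This agrees with the total in the conclusion.

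**4. The parts.** 68 + 67 = 135. The difference is 135 − 115 = 20, and 20 / 115 = 17.4%. This does not reproduce. Steps 1 to 3 are sound, so the fault lies in the breakdown or in a missing step before it.

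**5. Could an unstated allowance explain 135?** None is given in the protocol, and round figures do not land on it exactly:

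| Allowance | Calculation | Rounded up |
|---|---|---|
| 10% loss | 115 / 0.90 = 127.8 | 128 |
| 15% loss | 115 / 0.85 = 135.3 | 136 |
| 15% added | 115 × 1.15 = 132.25 | 133 |
| 20% added | 115 × 1.20 = 138 | 138 |

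A 15% loss comes close, but 135 × 0.85 = 114.75, just under 115. The loss that 135 can absorb is 20 / 135 = 14.8%. A slip for 58 + 57 = 115 is equally possible. The text settles neither.

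**6. What each total would deliver.** Half-width = 1.96 × 0.82 / √n. Power and detectable difference use the two-sided noncentral t at 5%.

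| Groups | Total | Half-width for the mean | Power for 0.79 | Detectable difference at 80% power |
|---|---|---|---|---|
| 58 / 57 | 115 | 0.150 | 98.7% | 0.53 |
| 68 / 67 | 135 | 0.138 | 99.5% | 0.49 |

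The half-widths treat the whole enrolled sample as contributing to the single mean. Both totals meet the precision of 0.15, and both far exceed the 80% power asked for at 0.79.

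**The case against.** The best defence is that *at least* sets a floor: 135 satisfies a minimum of 115, so the plan could be read as a floor of 115 with 68 and 67 as the planned groups. That reading is possible but does not fit the sentence. The word *comprising* makes the two groups the parts of the 115, and *Consequently* ties that total to the calculation just before it. Nothing in the protocol says that the planned number exceeds the calculated one, or why.

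A second defence is that the discrepancy does no statistical harm. That stands. Both totals meet the precision requirement and leave power for 0.79 above 98%.

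A reader might infer more than the document supports, in three ways.

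- **That the detectable effect is undefined or the comparison underpowered.** The protocol does state a design effect, 0.79 with 27 per group, and either total is more than twice the 54 this needs. Only the effect detectable at the planned enrolment is left open, within about 0.49 to 0.53 for the two balanced readings.
- **That the 54 is itself an error because the study will not enrol 54.** Section 5 calls it a minimum and says that the largest calculated size is used. Calculating a size for each objective and taking the largest is ordinary practice, and here it is openly stated.
- **That recruitment could stop at 115 with a lopsided split, such as 68 and 47.** The protocol contains no recruitment stopping rule and no such split. The only allocations it gives, 27 / 27 and 68 / 67, are balanced or nearly so.

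**Conclusion.** Wrong as written. The stated total of 115 and the stated groups of 68 and 67 differ by 20 participants, 17% of 115, and nothing in the protocol reconciles them. The arithmetic needs no assumption. The consequence is an ambiguous planned total and ambiguous group sizes, in the only sentence that fixes either. It is not a loss of power or of precision. That second statement rests on the assumed two-sided two-sample t-test and on the stated effect size of 0.79 and standard deviation of 0.82.

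It is tempting to conclude that 135 is 115 inflated for 15% loss. The figures are close, but the protocol gives no allowance and the arithmetic falls slightly short, so this remains a guess for the sponsor to confirm or reject. The correction should be made because the enrolment target is a figure that the trial relies on and the repair is cheap.

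**What to change.** Rewrite the last sentence of section 5 so that the total equals the sum of the groups. The sponsor must say which figure was intended.

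- **If 68 and 67 are the intended group sizes:** state a planned enrolment of 135, with 115 as the minimum evaluable number, and give the loss allowance actually used. The margin covers a loss of up to 14.8%. If a full 15% is wanted with at least 115 remaining, the total must be 136.
- **If 115 is the intended enrolment:** correct the group sizes so that they sum to 115, for example 58 + 57, and say whether any allowance for loss is made.

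Optionally, add the standardised difference detectable at 80% power for the chosen size: 0.49 at 68 / 67 or 0.53 at 58 / 57. This would be informative, but the existing calculation is not in error without it.

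The cost is one corrected sentence. Whether recruitment changes depends on which figure the sponsor has been working to: settling on 135 means 20 more participants than 115.

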STUDY PROTOCOL

Study name:	Effectiveness of enhanced recovery after surgery (ERAS) protocols for arthroscopic anterior cruciate ligament reconstruction in an ambulatory surgery setting
Duration:	April 16 th 2026 - April 16 th 2027

1. Study Description (Brief summary)

The anterior cruciate ligament (ACL) is a critical component for maintaining knee stability by resisting anterior tibial translation and internal rotation. ACL rupture is one of the most common orthopedic injuries, with an estimated incidence of 70 cases per 100,000 people annually [1]. Since its inception, arthroscopic anterior cruciate ligament reconstruction (AACLRL) has proven to be the gold standard, providing excellent outcomes in terms of graft longevity, return to sports, and patient satisfaction [2]. Modern medical trends are shifting toward day-surgery protocols, where patients are discharged within 24 hours without an overnight stay. This model is identified as a major factor in enhancing the quality of postoperative recovery and patient satisfaction [3].

The Enhanced Recovery After Surgery (ERAS) program utilizes evidence-based multimodal interventions to reduce surgical stress and accelerate functional recovery. While day-surgery for AACLRL has been proven feasible globally, its implementation in Vietnam remains limited due to systemic barriers [4,5]. At the University Medical Center Ho Chi Minh City, although ERAS has been applied since 2022, the average length of stay for AACLRL is 2.57 days, indicating significant room for optimization. This study aims to evaluate the current compliance with ERAS and the effectiveness of fully implementing these protocols to enable a day-surgery model.

The research is designed in two phases, including a descriptive cohort and a clinical intervention. The intervention focuses on 06 core ERAS measures:

- Comprehensive preoperative counseling and education.
- Reducing preoperative fasting by using Maltodextrin 2 hours before surgery.
- Standardized anesthesia combined with local infiltration analgesia (LIA).
- Multimodal analgesia to minimize opioid consumption.
- Early drainage removal within 6–8 hours postoperatively.
- Immediate postoperative rehabilitation starting in the recovery unit.

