Effectiveness will be measured through various outcomes: the quality of early recovery via the QoR-15 score, mechanical knee function via the Lysholm Knee Scoring Scale (LKSS), and health-related quality of life via the EQ-5D-5L. Furthermore, a cost-effectiveness analysis (CEA) will be conducted using the Incremental Cost-Effectiveness Ratio (ICER). The study expects to demonstrate that strict ERAS adherence makes day-surgery ACLR feasible, reduces hospital-acquired infections, optimizes operating room productivity, and lessens the financial burden on both patients and the healthcare system.

2. Objective

- 2.1. To describe the current status of ERAS program implementation among patients undergoing arthroscopic anterior cruciate ligament reconstruction (ACLR) at University Medical Center Ho Chi Minh City.
- 2.2. To evaluate the impact of ERAS interventions on postoperative recovery quality, cost-effectiveness, and the feasibility of implementing a day-surgery protocol for patients undergoing ACLR.

3. Materials and methods

Study design: Two-phase study

- Phase 1: Cross-sectional study, Retrospective cohort study.
- Phase 2: Interventional study.

Observational Model: Cohort

Actual study start date: April 16th, 2026

Actual study completion date: April 16th, 2027

4. Criteria

Inclusion criteria

- Patients aged 18 years and older.
- Diagnosis of anterior cruciate ligament (ACL) rupture with indication for primary arthroscopic reconstruction.
- Voluntary agreement to participate in the study and signing of the informed consent form.

Exclusion criteria

- Patients with concomitant knee pathologies requiring additional surgical procedures in the same session.
- Presence of contraindications for ambulatory (day) surgery.
- Failure to adhere to the scheduled follow-up visits.

- Incomplete medical records regarding the implementation of ERAS protocol components (for the retrospective phase).

5. Sample size

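### Objective 2.2 seeks the effect of ERAS on recovery quality and cost-effectiveness, but the only stated Phase 2 comparison, elective versus day surgery, cannot isolate that effect

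*Protocol*

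**What the plan says.** Objective 2.2 (Section 2) reads "To evaluate the impact of ERAS interventions on postoperative recovery quality, cost-effectiveness, and the feasibility of implementing a day-surgery protocol". The Study Description (Section 1) frames the aim as "the effectiveness of fully implementing these protocols to enable a day-surgery model" and records that at this hospital "although ERAS has been applied since 2022, the average length of stay for AACLRL is 2.57 days".

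Section 6, Phase 2, gives two instructions that together fix the design. The intervention is to "Apply 06 standardized ERAS measures to the patients". The comparison is to "Monitor and compare outcome variables between elective surgery and day-surgery groups, including recovery quality, complication rates, and cost-effectiveness". Enrolment in Section 5 is divided on the same line, into 68 elective and 67 day-surgery cases. No group is described as receiving usual care, partial ERAS or no ERAS, and no allocation rule is given.

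Phase 1 is to "Perform a cross-sectional descriptive study to evaluate the quality of postoperative recovery using the QoR-15 tool", together with knee function and EQ-5D-5L. It is labelled descriptive, and no comparison of Phase 1 with Phase 2 is stated.

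**The concern.** The intervention is defined by ERAS, but the comparison is defined by discharge pathway. A two-group difference can speak to ERAS only if the groups differ in ERAS and in little else. As written, either they do not differ in ERAS at all, or they differ in ERAS and pathway together.

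The recovery and cost-effectiveness conclusions are at stake. A report that follows objective 2.2 would credit ERAS with a difference that belongs to the pathway, or to a mixture of the two. The ICER has the same problem, because its incremental cost and incremental benefit are both taken from this contrast. Who receives the intervention, and against whom they are compared, is core design that the protocol sets in Section 6. A statistical analysis plan cannot supply a comparator that the design does not contain.

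**Working it through.** **1. The plan's own figure.** Section 5 says "a minimum of 54 patients (27 per group) is required" for an effect size of 0.79, 80% power and a significance level of 0.05.
- Normal approximation, two-sided: n per group = 2(1.960 + 0.842)² / 0.79² = 15.70 / 0.624 = 25.2, so 26.
- Two-sample t-test (noncentral t, two-sided, 1:1): n = 26.15, so 27 per group and 54 in total. Power at 27 per group is 81.3%.

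The figure reproduces. It is a calculation for a difference between two groups, and the only groups the protocol names are elective and day surgery.

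**2. What that difference estimates.** For one outcome, let
- m = the mean under existing practice with elective stay,
- e = the effect of the six measures relative to existing practice (existing practice is already some ERAS, since "although ERAS has been applied since 2022"),
- p = the effect of the day-surgery pathway,
- b = residual selection between the groups.

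| Who receives the six measures | Elective mean | Day-surgery mean | Day minus elective |
|---|---|---|---|
| Both groups (literal reading) | m + e | m + e + p + b | p + b |
| Day-surgery group only (not stated) | m | m + e + p + b | e + p + b |

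*Both groups.* For e = 0.2, 0.5, 0.79 or 1.0 SD, the contribution of ERAS to the contrast is e − e = 0 each time.

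*Day-surgery group only.* An observed difference of 0.79 SD fits e = 0.79 with p + b = 0, e = 0.20 with p + b = 0.59, and e = 0 with p + b = 0.79. The data cannot choose among these.

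**3. The ICER.** ICER = (cost difference) / (benefit difference), each day surgery minus elective. On the first reading, the cost and the benefit of the six measures drop out of both terms. On the second, both terms belong to ERAS and pathway together.

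**4. Sample size does not repair this.** With 68 versus 67, power at 0.79 is 99.5%, and the effect detectable with 80% power is about 0.49. The precision improves, but the quantity estimated is unchanged.

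**5. What does not need the contrast.** Day-surgery feasibility can be described within the ERAS-treated day-surgery patients. Section 6 plans a discharge-readiness score (PADS), complication rates and 7-day readmission.

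**The case against.** **The package may be the intended target.** The title places ERAS in an ambulatory setting, and Section 1 presents full implementation as the means to day surgery. If the day-surgery group gets full ERAS and the elective group gets existing care, the sum of the two effects could be what the sponsor wants. This is fair, and the protocol does not exclude it. It does not state it either, and objective 2.2 attributes the effect to ERAS, not to a package. The remedy on this reading is clarification and a narrower conclusion.

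**A reader might infer that the comparison is wholly confounded.** That goes too far. Section 4 excludes patients with contraindications to day surgery and does not limit this to one group, so elective patients must also be eligible for day surgery. A pre-operative assessment (T-1) is also collected in Phase 2. Some selection remains possible because no allocation rule is given.

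**A reader might infer that objective 2.2 goes unanswered altogether.** It does not, because its feasibility part can be described without any ERAS contrast.

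**A reader might infer that comparing Phase 2 with Phase 1 is a ready and cheap repair.** The protocol does not support this. It lists T-1 collection only under Phase 2 and states no pre-operative scores or costs for Phase 1. It does not say that the Phase 1 cross-sectional patients are treated under current practice. Section 5 derives 115 for the cross-sectional sample and then gives one enrolment target, and the timetable in Section 7 has a single data-collection year. The two sets of patients may be the same people.

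**The algebra assumes additive effects and equal delivery of ERAS in both groups.** This is true. With an interaction, the first reading gives the pathway effect under ERAS, which is still not an ERAS effect. With unequal adherence, an unknown fraction of e enters the contrast and cannot be separated from the rest.

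**Conclusion.** The point holds for the recovery-quality and cost-effectiveness parts of objective 2.2. On the literal reading, the stated contrast carries no ERAS effect, whatever its true size. On the unstated alternative, it gives ERAS and pathway combined, plus residual selection that the day-surgery exclusion criterion reduces but does not remove. Neither reading yields an isolated ERAS effect, and the sample size has no bearing on this.

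The conclusion rests on three features of the text: no group is named as not receiving the six measures, no other Phase 2 comparison is stated, and no allocation rule is given. If the sponsor confirms a different arrangement, the second row of the table or a before-after comparison may apply, and the permitted conclusion changes accordingly. Feasibility stays outside the criticism.

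**What to change.** 1. State in Section 6 which group or groups receive the six measures, how patients come to be in the elective or day-surgery group, and what the other group receives if it does not get all six.
2. Reword objective 2.2 and define the ICER to match. If both groups receive the measures, the recovery and cost-effectiveness conclusions concern day surgery versus elective stay under ERAS. If only one does, they concern the combined ERAS and day-surgery package. Keep feasibility as a separate, descriptive aim.
3. Adjust the comparison for the T-1 values that Phase 2 already plans to collect, and report it as non-randomised unless allocation is randomised.
4. Add a before-after contrast of full versus existing ERAS only if the sponsor confirms that the Phase 1 cross-sectional patients are a separate current-practice cohort assessed at the T1 time point.

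Items 1 to 3 cost protocol wording and an adjusted analysis of data already planned. Item 4 is not free: pre-operative scores and costs are not stated for Phase 1, so it could require new measurement or a new cohort, and it would still be a non-randomised comparison. The scientific price is that the Phase 2 comparison can then support no claim of an isolated ERAS effect on recovery or cost.
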